#### **7.2.4 Clotting in the Drip Chamber and Dialysis Filter**

Visual inspection of clotting in the drip chamber will be recorded 2 hours after start of dialysis and at the end of dialysis on Days -7, -5, -3, 1, 3, 5, and 12.

Visual inspection of clotting in the dialysis filter will be recorded at the end of dialysis on Days -7, -5, -3, 1, 3, 5, and 12.

Summary of clotting values will be listed and summarized by treatment and Day in Tables for all subjects in the Safety Population (2 active dose levels and pooled placebo).

#### **7.2.5 Dialysate Analysis**

A 10 mL dialysate sample will be taken at the start and at the end of HD on Days -7, -5, 3, 12 and at 0.5 and 4 hours post dosing on Day 1.

The samples will be sent to Aronora and will be stored for up to 5 years following the last dosing for future analysis (e.g., xisomab 3G3 levels and or urea).

### **8. SAFETY**

All case report form (CRF) data will be listed by subject and chronologically by assessment time points. This will include rechecks, unscheduled assessments, and early termination.

Applicable continuous variables will be summarized using n, arithmetic mean, SD, minimum, median, and maximum. Data from subjects who received the placebo treatment will be pooled across cohorts.

The level of precision will be presented as follows: minimum/maximum in the same precision as in the database, mean/median in one more precision level than minimum/maximum, SD in one more precision level than mean/median, and n will be presented as an integer. Percentages of total frequency counts, if presented, will be reported as whole numbers.

Where individual data points are missing because of dropouts or other reasons, the data will be summarized based on reduced denominators.

#### **8.1 Subject Discontinuation**

Subjects will be summarized by number of subjects dosed, completed, and discontinued the study with discontinuation reasons by treatment (two dose levels and pooled placebo and study overall).

## **8.2 Demographics**

Descriptive statistics will be calculated for continuous variables (age, weight, height, and body mass index) and frequency counts will be provided for categorical variables (race, ethnicity, and sex) by treatment and overall. Age will be derived from date of birth to date of first dosing.

## **8.3 Adverse Events**

All adverse events (AEs) occurring during this clinical trial will be coded using the Medical Dictionary for Regulatory Activities (MedDRA®), Version 21.1.

All AEs captured in the database will be listed in by-subject data listings including verbatim term, coded term, treatment, severity, relationship to study medication, and action; however, only treatment-emergent AEs (TEAEs) will be summarized.

A TEAE is defined as an AE that is starting or worsening at the time of or after study drug administration. Each TEAE will be attributed to a treatment based on the onset date and time of the AE. If the onset time of an AE is missing and the onset date is the same as the treatment dosing date, then the AE will be considered treatment emergent. If the onset date of an AE is missing, then the AE will be considered treatment emergent.

TEAEs will be tabulated by System Organ Class (SOC) and Preferred Term. Summary tables will include number of subjects reporting the AE and as percent of number of subjects dosed by treatment and overall. The number of AEs will be tabulated in a similar manner. Tables which tabulate the number of TEAEs by severity and relationship to study treatment will also be included.

Serious adverse events (SAEs), if present, will also be listed. Applicable narratives will be included in the CSR.

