A placebo arm is included in this study design in order to robustly demonstrate the safety and efficacy of xisomab 3G3 while not placing the subjects at unnecessary risk, as mentioned above. The primary endpoint in this study is safety, measured as the number of adverse events that occur during the observation period. A heparin free inpatient HD observation period (Study Days -7 to 1) is included in the trial design to establish a baseline for the heparin-free procedure. Continuation of the heparin-free HD procedure during the subsequent trial period and inclusion of a placebo arm allows for the determination of whether an adverse event is drug-related or not and permits accurate assessment of the safety of the study drug. The addition of a placebo arm also removes potential bias from the interpretation of AEs by the PIs and the subjects. The secondary endpoint for this study is efficacy of xisomab 3G3 on hemodialysis efficiency which may be more clearly observed with a placebo control instead of an active control (e.g., heparin). While the placebo arm may be at the same risk of clotting within the dialysis circuit as during the pre-dosing period (Study Days -7 to 1), data cited above suggests that these patients will not be at higher risk for either thromboembolic or bleeding complications. Should clotting occur within the dialyzer cartridge during a hemodialysis session that results in dialyzer failure, the dialyzer cartridge will be replaced, and the patient will be closely monitored by the PI. It is important to note that replacement of the dialyzer cartridge during HD is safe for the patient and a routine procedure in cases of dialyzer failure.

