9.2 Endpoints

Primary outcome measures:

- The safety and tolerability of xisomab 3G3 will be evaluated versus pre-treatment and placebo by reviewing number and severity of adverse events and use of concomitant medications, physical examination, vascular access site reaction, bleeding time, and changes in vital signs, ECGs, and clinical laboratory evaluations.

Secondary outcome measures:

- PD using dose-dependency of drug potency, determined by measuring changes in coagulation parameters, and thrombus accumulation (assessed and ranked by visual inspection) within the dialyzer cartridges and total protein accumulation in the HD filter after xisomab 3G3-treatment versus pre-treatment and placebo.
- Efficacy on hemodialysis efficiency using BUN and potassium levels before and after hemodialysis, length of HD, measurement of urea removed by 3 hours of dialysis, and total dialysate urea (single pool Kt/V and URR) after xisomab 3G3-treatment versus pre-treatment and placebo.

Other outcome measures:

- PK parameters of xisomab 3G3, calculated, as appropriate: AUC0-t, AUC0-inf, AUC%extrap, Cmax, Tmax, Kel, t^{1/2}, CL, and Vss.
- Development of immunity or antibodies against xisomab 3G3 after drug exposure.

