13.2.8.2 Monitoring

Patients will be monitored for AEs from check-in through completion of the study. Patients will be asked how they are feeling once per day during confinement and at each return/follow-up visit.

AEs (whether serious or non-serious) and clinically significant abnormal laboratory test value(s) will be evaluated by the PI or designee and treated and/or followed up until the symptoms or value(s) return to normal, or acceptable levels, as judged by the PI or designee.

Treatment of serious adverse events (SAEs) will be performed by a licensed medical provider, either at the CRU or at a nearby hospital emergency room. Where appropriate, medical test(s) and/or examination(s) will be performed to document resolution of event(s). Outcome may be classified as resolved, improved, unchanged, worse, fatal, or unknown (lost to follow-up).

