13.2.8.3 Reporting

All AEs that occurred during this clinical study (i.e., before, during, and after exposure of ESRD patients to xisomab 3G3) will be recorded. This design is to improve Sponsor ability to obtain reliable initial information about drug safety yet reducing the number of study patients needed to generate useful data.

Adverse events and SAEs that are related to study participation (e.g., protocol-mandated intervention) will be recorded from the time the patient check-in until study completion. All other AEs and SAEs will be recorded from Day -8 until exit from the study.

AEs will be coded using the most current MedDRA® available at Celerion.

The PI or designee will review each event and assess its relationship to study drug (likely, probably, possibly, unlikely, or unrelated) and severity. The date and time of onset, time relationship to drug dosing, duration, and outcome of each event will be noted.

Relationship of AE:

The relationship of each AE to the study drug will be assessed using the following definitions:

| | |
|-----------|--|
| Unrelated | 
 The adverse event must clearly be caused by the participants clinical state, or the study procedure/conditions Definitely not related to drug Temporal sequence of an adverse event onset relative to administration of drug not reasonable Another obvious cause of an adverse event |
| Unlikely | 
 Time sequence is unreasonable There is another more likely cause for an adverse event |
| Possibly | 
 Corresponds to what is known about the drug Time sequence is reasonable Could have been due to another equally, likely cause |
| Probably | 
 Is a known effect of the drug Time sequence from taking drug is reasonable Ceases on stopping the drug Cannot be reasonably explained by the known characteristics of the participants clinical state |
| Likely | 
 Is a known effect of the drug (e.g. listed in IB) Time sequence from taking drug is reasonable Event stops upon stopping drug, event returns upon restarting drug 
Note: Prolonged aPTT is an expected pharmacological effect of xisomab 3G3 and will, therefore, not be considered an AE.
 |

Severity of AE:

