### 2.2 Endpoints

#### Primary outcome measures:

- The safety and tolerability of xisomab 3G3 will be evaluated versus pre-treatment and placebo by reviewing number and severity of adverse events and use of concomitant medications, physical examination, vascular access site reaction, bleeding time, and changes in vital signs, ECGs, and clinical laboratory evaluations.

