## **9. SUMMARY OF CHANGES FROM PROTOCOL-PLANNED ANALYSIS**

The length of HD was 3 hours in the protocol and should be approximately 4 hours. The samples collected for BUN and potassium will be at the end of dialysis (approximately 4 hours).

The analyses described in this SAP are aligned with those analyses described in the protocol.

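### The primary outcome compares adverse events with pre-treatment, but every planned adverse event summary is limited to events after dosing

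*SAP*

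**What the plan says.** **Endpoint.** SAP Section 2.2 gives the primary outcome as follows: "The safety and tolerability of xisomab 3G3 will be evaluated versus pre-treatment and placebo by reviewing number and severity of adverse events". Protocol Section 9.2 has the same comparator: safety "will be evaluated versus pre-treatment and placebo by reviewing number and severity of adverse events". Other safety measures follow in the same sentence, but AEs come first.

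**Purpose of the run-in.** Protocol Section 8.4.1 says: "A heparin free inpatient HD observation period (Study Days -7 to 1) is included in the trial design to establish a baseline". Protocol Section 13.2.8.2 says: "Patients will be monitored for AEs from check-in through completion of the study". Section 13.2.8.3 has AEs recorded before, during and after exposure and gives the reason: "This design is to improve Sponsor ability to obtain reliable initial information about drug safety yet reducing the number of study patients needed".

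**Analysis.** SAP Section 8.3 sends all recorded AEs to by-subject listings and then adds: "however, only treatment-emergent AEs (TEAEs) will be summarized". A treatment-emergent AE (TEAE) is one that begins or worsens at or after dosing. Protocol Section 14.3.1 likewise specifies counts of patients with TEAEs and of TEAEs by treatment, and no other AE summary.

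**Outputs.** Tables 14.3.1.1 to 14.3.1.3 are titled as treatment-emergent. Table 12-1 has a general AE title, but its rows count TEAEs. The columns (rows, in Table 14.3.1.3) are the two dose levels, pooled placebo and overall. Run-in AEs appear in Appendices 16.2.7.1.1, 16.2.7.1.2 and 16.2.7.2, which carry a TE? flag and the onset date and time, and in Table 14.3.2.1 if serious.

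**The concern.** Summarising TEAEs only is ordinary practice when events before dosing are incidental. Here they are not. The endpoint names pre-treatment as a comparator for AEs, and the protocol presents recording before exposure as part of what lets a small trial give useful safety information. Protocol Section 8.5 warns that these patients are prone to a wide range of events on or off dialysis, so the background rate matters when TEAE counts are read.

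If the plan is followed exactly, the report will have no summary that sets a patient group's AEs after dosing against the same group's AEs on heparin-free dialysis before dosing. If someone builds that summary later, the window, the denominator and the handling of undosed patients will be chosen after the results are known. SAP Section 1 treats analyses not described in the SAP as outside its scope.

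**Working it through.** The plan gives no figure to reproduce on this point, and protocol Section 14.1 says the sample size had no statistical basis. The check is a trace through the documents, followed by a count of the observation time involved.

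**1. Trace**

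| Step | Place | Pre-dose AEs included? |
|---|---|---|
| Endpoint | Protocol 9.2, SAP 2.2 | Yes, as comparator |
| Collection | Protocol 13.2.8.2, 13.2.8.3 | Yes, from Day -8 |
| Analysis rule | Protocol 14.3.1, SAP 8.3 | No |
| Frequency tables | 12-1, 14.3.1.1, 14.3.1.2, 14.3.1.3 | None of 4 |
| Listings | 16.2.7.1.1, 16.2.7.1.2, 16.2.7.2 | Yes, flagged |

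The chain breaks at the analysis rule, in both documents.

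**2. Windows per patient**

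There is no Day 0, since protocol Section 10.1 places Day -7 one week before dosing on Day 1. Session days come from flow chart footnote d.

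- Before dosing: Days -8 to -1 = 8 days, with 3 sessions (Days -7, -5, -3).
- From dosing on: Days 1 to 12 = 12 calendar days, or 12 - 1 = 11 elapsed days, with 6 sessions (Days 1, 3, 5, 8, 10, 12).
- Share of days outside every AE summary: 8/(8+11) = 42%, or 8/(8+12) = 40%.
- Share of sessions: 3/(3+6) = 33%.

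**3. Exposure by group**

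Two cohorts of 9 to 12 at 2:1 give 18 to 24 patients: 6 to 8 per active dose and 6 to 8 pooled placebo.

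- One group before dosing: 6×8 = 48 to 8×8 = 64 patient-days; 6×3 = 18 to 8×3 = 24 sessions.
- One group from dosing on: 6×11 = 66 to 8×12 = 96 patient-days; 6×6 = 36 to 8×6 = 48 sessions.
- All patients before dosing: 18×8 = 144 to 24×8 = 192 patient-days; 18×3 = 54 to 24×3 = 72 sessions.

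**4. Why raw counts would not do**

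With no drug effect and a constant rate per day, the later window would show 11/8 = 1.375 to 12/8 = 1.5 times as many events. With a constant rate per session it would show 6/3 = 2 times as many.

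**5. Scale of procedure events**

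Protocol Section 8.4.1 cites dialyzer exchange in 5 to 7% of heparin-free procedures. If that rate applied here and all patients completed the run-in, 54×0.05 = 2.7 to 72×0.07 = 5.0 exchanges would be expected before dosing. This is only an illustration, because an exchange need not be recorded as an AE.

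**The case against.** The strongest reply is that the endpoint speaks of reviewing AEs and promises no table. The listings give severity, onset time and a TE? flag, so the review can be done by hand. An event that begins in the run-in and worsens after dosing already counts as a TEAE. Placebo patients have the same heparin-free dialysis on the same schedule, so the concurrent control separates drug from procedure events at group level. All of this stands, and it limits the point. It does not supply the comparison the endpoint names, because a listing with a flag is not a summary.

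A reader might also infer more than the documents support:

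- *That half of the primary comparison is missing.* The primary outcome is a bundle. Bleeding time, vital signs, ECG and laboratory summaries show pre-dose values. The gap is the AE component against one of two comparators.
- *That SAP Section 9 is wrong to say* "The analyses described in this SAP are aligned with those analyses described in the protocol". On this point the statement is true of protocol Section 14.3.1, which is also limited to TEAEs. The mismatch is between the endpoint and the analysis sections of both documents.
- *That a patient withdrawn before dosing appears nowhere.* The AE listings are titled for the Safety Population, meaning dosed patients. But SAP 8.3 says every recorded AE will be listed, and protocol Section 11.3 requires the report to give reasons and details for withdrawals. The titles and the text need reconciling; the documents do not show that these events would be lost.
- *That the omitted reference is twice the size of placebo.* 144/72 = 2 in patient-days (6 placebo patients × 12 days = 72), but this sets every patient's run-in against one group's follow-up. Within one group, the run-in is the shorter window.

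**Conclusion.** For the AE component, the plan names a comparison with pre-treatment, collects the data for it, and schedules no summary that makes it. The omission follows from a stated rule in both analysis sections and is confirmed by all four frequency tables. About 40 to 42% of each patient's AE observation days and a third of the dialysis sessions fall outside every AE summary, assuming the patient completes the schedule.

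This is a reporting gap. No estimate is wrong, no power figure changes, and run-in events of dosed patients remain in the listings. It is worth closing before unblinding because the comparison belongs to the primary outcome and its denominators should not be chosen after the results are seen.

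**What to change.** **SAP Section 8.3.** Replace the restriction to TEAEs with a rule that also summarises pre-dose AEs, meaning onset from check-in on Day -8 to the start of study drug. Give patients, events and severity by system organ class and preferred term, by later treatment and overall, beside the TEAE results. Keep the drug-relationship part of Table 14.3.1.3 for TEAEs, since relationship to a drug not yet given has no meaning. State how an event that starts in the run-in and worsens after dosing is counted.

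**Denominators.** Alongside counts, give the rate per patient-day or per dialysis session, and fix whether follow-up is taken as 11 or 12 days.

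**Undosed patients.** Footnote that columns by later treatment include only patients who reached dosing and may understate run-in events. List separately the AEs of patients who checked in but were not dosed, and bring the listing titles into line with the Section 8.3 text.

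**SAP Section 9.** Record the addition as an extension of protocol Section 14.3.1, made to meet the protocol Section 9.2 endpoint.

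**Cost.** SAP wording and one more descriptive table, from data already collected. The small downside is a table whose two windows differ in length, which the rates address. The alternative is to drop pre-treatment as a comparator for AEs. That would change the primary endpoint, and protocol Section 14.3 requires major changes of that kind to be reflected in a protocol amendment.

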Xisomab 3G3 is expected to prevent pathologic thrombogenesis by selectively inhibiting thrombotic contact pathway activation without interrupting normal hemostasis or the hemostatic feedback activation of FXI by thrombin, or other mechanisms. As both thromboembolism and bleeding are common comorbidities in ESRD patients, safe anticoagulation is currently an unmet need for this patient population. Xisomab 3G3 is a fundamentally novel anticoagulant that is expected to reduce clot formation in vascular devices, including the hemodialyzer apparatus, without the increased risk of bleeding associated with heparin. In addition, data to date suggest that xisomab 3G3 may also reduce the incidence and severity of thromboembolic events in these patients. Further, non-clinical data suggest that xisomab 3G3 reduces systemic inflammatory responses, which may be detrimental, and has been associated with contact activation of the blood that is perfused through devices during external organ support. As such, xisomab 3G3 stands as a promising alternative to other anticoagulants in this population. It is therefore of interest to assess xisomab 3G3 safety and effectiveness in ESRD patients on chronic HD.

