8.5 Risks and/or Benefits to Patients

ESRD patients are often ill, and are prone to a variety of adverse events on or off HD, ranging, for example, from infections to hypertension to bleeding to thromboembolism to acute ischemic cardiovascular emergencies, even if they are apparently stable on chronic HD. A temporal and modest increase in blood pressure was observed in one study subject in the FIH study after xisomab 3G3 administration, and the event was deemed potentially related to the study drug.

Xisomab 3G3 is a purified protein produced by recombinant DNA technology in a mammalian cell culture system, and these types of drugs can, occasionally and unpredictably evoke acute allergic reactions. Some ESRD patients develop chronic HD- and uremia-related moderate hemorrhagic diathesis or hemostasis impairment. Even though currently available data do not indicate a hemostatic function for the FXI/FXII interaction, there remains a theoretical possibility of contact activation-mediated enhancement of hemostasis. Thus, the hemostatic safety of xisomab 3G3 in the complex conditions of ESRD and chronic HD is not yet known. The safety monitoring practices employed by this protocol (i.e., 12-lead ECG, vital signs, blood pressure, clinical laboratory tests, AE questioning, vascular access site (AV fistula or AV graft) monitoring, and physical examination) are adequate to protect the patients' safety and should detect all expected and unexpected treatment-emergent AEs (TEAEs). In addition, the cohorts will be dosed in a sequential manner, starting with the lower dose level, Cohort 1.

Patients undergoing heparin-free HD may be at higher risk of developing clots within the hemodialyzer. Should this occur, site standard operating procedures will be followed to replace the clotted dialyzer and resume HD under the supervision of the PI. It is important to note that replacement of the dialyzer cartridge is a safe procedure for the patient. While studies suggest that there is no risk of thromboembolic complications should this occur, clotting of the dialyzer circuit could result in up to ~228 mL of blood loss.

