## 1. INTRODUCTION

The following statistical analysis plan (SAP) provides the framework for the summarization of the data from this study. The SAP may change due to unforeseen circumstances. Any changes made from the planned analysis within the protocol, after the unblinding, or locking of the database will be documented in the clinical study report (CSR). The section referred to as Table Shells within this SAP describes the traceability of the tables, figures, and listings (TFLs) back to the data. Note that the header for this page will be the one used for the main body of the CSR.

Any additional exploratory analyses not addressed within this statistical analysis plan (SAP) and/or driven by the data, or requested by Aronora Inc., will be considered out of scope and must be described in the CSR.

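### No grouped count of bleeding or thromboembolic TEAEs by arm is planned, although hemostatic safety is the trial's stated open question, and the SAP drops the protocol's access-site bleeding incidence

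*SAP*

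**What the plan says.** Protocol 8.5 leaves hemostatic safety open: "the hemostatic safety of xisomab 3G3 in the complex conditions of ESRD and chronic HD is not yet known". Protocol 8.4.1 expects the drug to reduce clotting in devices "without the increased risk of bleeding associated with heparin", and adds that "data to date suggest that xisomab 3G3 may also reduce the incidence and severity of thromboembolic events in these patients". The primary outcome in SAP 2.2 reads: "The safety and tolerability of xisomab 3G3 will be evaluated versus pre-treatment and placebo by reviewing number and severity of adverse events". Prolonged aPTT is not an adverse event (protocol 13.2.8.1).

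For adverse events, SAP 8.3 states: "TEAEs will be tabulated by System Organ Class (SOC) and Preferred Term". It continues: "Tables which tabulate the number of TEAEs by severity and relationship to study treatment will also be included". The shells for Tables 12-1 and 14.3.1.1 to 14.3.1.3 follow this plan. The frequency tables have columns for each dose, pooled placebo and Overall.

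Other sections bear on the same question:

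- SAP 8.10 and Table 12-5 summarise access-site time to clot by treatment and timepoint.
- SAP 7.2.4 and Tables 11-7, 11-8, 14.2.6.1 and 14.2.7.1 summarise drip-chamber and filter clotting grades by treatment and day.
- SAP 8.9 covers access-site reactions. New abnormal findings there become adverse events.
- Protocol 14.3.1 plans to count both the incidence and the duration of access-site bleeding, and to compare treatment with pre-treatment and placebo.

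**The concern.** Bleeding is not one organ class. Gastrointestinal bleeding, nosebleeds, blood in the urine and bruising code to different classes and terms, as do access thrombosis and embolic events. A table built on those rows does not answer the clinical question of how many patients in each arm bled, or how many had a thromboembolic event. In arms of 6 to 8 patients, an excess made up of different terms can look like unrelated single events.

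Timing matters too. SAP 1 says that analyses not in the plan "will be considered out of scope and must be described in the CSR". A grouping made after unblinding would be a choice made with the results in view, and it could move the answer either way.

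**Working it through.** The plan states no bleeding rate, thrombosis rate, power or alpha, and protocol 14.1 says the sample size had no statistical basis. There is therefore no planned figure to reproduce.

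**1. Arm sizes** (protocol 14.1: 9-12 per cohort, 2:1, two cohorts; placebo pooled under 14.3.1).
- Active per dose: 9 × 2/3 = 6 to 12 × 2/3 = 8.
- All active: 2 × 6 = 12 to 2 × 8 = 16.
- Pooled placebo: 2 × 3 = 6 to 2 × 4 = 8.
- The Overall column holds 18 to 24 patients, one third of them on placebo. It cannot serve as an all-active count.

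**2. What each output counts.**

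| Output | Unit | Any-bleeding count by arm? | Any-thromboembolic count by arm? |
|---|---|---|---|
| Tables 12-1, 14.3.1.1 | patients per class and term | no | no |
| Table 14.3.1.2 | events per class and term | no | no |
| Table 14.3.1.3 | patients and events per term, with severity and relationship | no | no |
| SAP 8.10, Table 12-5 | time to clot at the access site | no | no |
| SAP 7.2.4 tables | clotting grade in chamber and filter | no | no (circuit only) |

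Neither document defines a bleeding or thromboembolic event group, an event of special interest or a standardised MedDRA query.

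**3. What grouping shows (illustration).** Suppose three of 8 patients bleed, each with a different term. The preferred-term rows read 1/8 = 13% three times. Grouped, the count is 3/8 = 38%, Clopper-Pearson 95% CI 8.5-75.5%.

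**4. Zero events.** The two-sided 95% upper limit is 1 − 0.025^(1/n).
- n = 6: 46%; n = 8: 37% (one dose).
- n = 12: 26%; n = 16: 21% (all active).

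**5. How often rows would hide a cluster.** Assumptions, none from the documents: each patient bleeds with risk p, each bleeder has one term, and terms are spread evenly over k = 3 to 6. The chance that no term row in an arm has two or more patients is

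Σₓ C(n,x) pˣ (1−p)ⁿ⁻ˣ × k!/[(k−x)! kˣ].

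For n = 8, p = 0.25, k = 4 the terms for x = 0 to 4 are 0.1001 + 0.2670 + 0.2336 + 0.0779 + 0.0081 = 0.687. Over k = 3 to 6:
- p = 0.25: 0.76-0.86 (n = 6) and 0.62-0.77 (n = 8).
- p = 0.50: 0.34-0.55 (n = 6) and 0.16-0.35 (n = 8).

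These include arms with no bleeder or one, where there is nothing to scatter. Given at least two bleeders, the example becomes (0.2336 + 0.0779 + 0.0081)/(1 − 0.1001 − 0.2670) = 0.505. The same conditioning gives 0.40-0.71 at p = 0.25 and 0.13-0.50 at p = 0.50, over both arm sizes. Scatter is a real possibility at moderate risk, not a certainty.

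**6. What grouping cannot do.** Fisher's exact test gives p = 0.20 for 3/8 v 0/8 and p = 0.28 for 4/8 v 1/8. Two-sided p < 0.05 needs at least 5/8 v 0/8, or 8/16 v 0/8 with the doses pooled.

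**7. Protocol against SAP on access-site bleeding.** Protocol 14.3.1 has incidence and time. SAP 8.10 has time only, while SAP 9 says its analyses are aligned with the protocol. The bleeding-time output is also loosely specified. A shell note sources Table 12-5 to coagulation Table 14.3.5.5. Another refers to a Section 14.3 bleeding-time table that SAP 10.2 does not list, and adds Days 8 and 10, which SAP 8.10 does not schedule.

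**The case against.** The strongest objection is that the plan already compares both risks by arm. Time to clot is summarised by treatment, and circuit clotting is counted by grade up to complete occlusion. Access-site reactions are assessed, organ-class rows count each patient once, and severity tables, listings and SAE narratives are planned. With at most 24 patients, every event can be read individually. Protocol 14.3 allows additional analyses, and the trial is descriptive.

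Much of this stands. A reader might infer that bleeding and thrombosis are not compared between arms at all, or that time to clot is the only look at the access site. The documents do not support either reading. Nor do they bar later grouping: SAP 1 requires only that it be described. Organ-class rows do collect terms within the same class, which makes scatter there less than the term-row model suggests.

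The existing outputs still do not fill the gap. Time to clot and circuit grades describe the needle site and the extracorporeal circuit. They do not count systemic bleeding, access thrombosis or embolic events. Listings let a reader group terms, but by no rule fixed in advance.

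The case against a broad composite is also sound. Minor puncture-site bleeding is expected at dialysis (protocol 11.2, criterion 9), so counting all of it could fill every arm. Circuit clotting is a pharmacodynamic measure with its own tables, and protocol 8.4.1 distinguishes it from thromboembolic complications.

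**Conclusion.** The gap is real and modest. The primary outcome is safety and the declared unknown is hemostatic, yet no table states how many patients in each arm had any bleeding TEAE or any thromboembolic TEAE, and no all-active count exists. The SAP also omits, without saying so, an access-site bleeding incidence that the protocol promised.

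The size is a matter of visibility. A 38% rate can be displayed as three rows of 13%. A finding of no events would carry no stated limit, though the exact one is 37-46% per dose and 21-26% for all active patients. The scatter figures rest on assumed risks and an even spread of terms. The all-active limits treat the two doses as sharing one risk.

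A reader might go further and infer that a bleeding excess would be missed, or that grouping would give a test of it. Neither follows. Scatter depends on rates the documents do not give, and at these sizes only extreme splits reach significance.

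**What to change.** In SAP 8.3, before unblinding, fix two MedDRA-based term lists:

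- **Any bleeding TEAE**, with access-site bleeding included only when reported as an adverse event.
- **Any thromboembolic or vascular-access thrombosis TEAE**, leaving circuit clotting in its existing pharmacodynamic tables.

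For each list, report patients with at least one event, and with at least one of Grade 2 or higher. Show each dose, all xisomab 3G3 and pooled placebo, with exact 95% intervals, labelled descriptive.

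In SAP 8.10, restore access-site bleeding incidence by arm against pre-treatment and placebo, with a stated threshold. One candidate is bleeding still present at the first check, 10 minutes after needle removal (protocol 13.2.6). List the bleeding-time source table in SAP 10.2, and align its days with SAP 8.10.

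The grouped counts need one paragraph and one table from adverse events already coded. The incidence uses bleeding times already collected. The costs are agreeing the lists and threshold in advance, and an all-active row that pools two doses with different expected durations of activity (protocol 8.4.2). Showing each dose beside it limits that drawback.
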